### **6.3.2. Breaking the Blind**

The IRT will be programmed with blind-breaking instructions. In case of an emergency, the investigator has the sole responsibility for determining if unblinding of a participant's treatment assignment is warranted. Participant safety must always be the first consideration in making such a determination. If the investigator decides that unblinding is warranted, the investigator should make every effort to contact the sponsor prior to unblinding a participant's treatment assignment unless this could delay further management of the participant. If a participant's treatment assignment is unblinded, the sponsor must be notified within 24 hours after breaking the blind. The date and reason that the blind was broken must be recorded in the source documentation and case report form (CRF).

The study-specific IRT reference manual and IP manual will provide the contact information and further details on the use of the IRT system.

### **6.4. Study Intervention Compliance**

Participant compliance with IP will be assessed at each visit as noted in the [SoA](#).

Compliance will be assessed by counting returned tablets. Through Visit 8, which occurs during the first 10 weeks of dosing when participants may be receiving titrated doses as part of their blinded regimen, sites should assess the blister cards for compliance; however, the cards should remain in the possession of the participant. Compliance (as assessed by tablet count) will be defined as self-administration, by the participants, of:

- $\geq 89\%$  of the study-supplied placebo administered during the single-blind placebo run-in period. Based on the visit window, for a placebo run-in that is 11-13 days, up to 2 missed doses are allowed, and for a placebo run-in that is 14-17 days, up to 3 missed doses are allowed. Participants who do not meet this compliance threshold are not eligible to be randomized into the study (See [Section 5.2](#)).
- $\geq 80\%$  of the study-supplied IP from Day 1 (Visit 3) through Week 12 (Visit 9), inclusive. Investigators must closely follow non-compliant, randomized, participants to enhance their adherence to treatment. Any participant who fails to meet the criterion of  $\geq 80\%$  compliance will be re-educated by the site staff on the importance of compliance with IP.

Deviation(s) from the prescribed dosage regimen should be recorded in the CRF.

## **6.5. Concomitant Therapy**

Participants in this study will be allowed to be on certain concomitant medications that have been prescribed. Attempts should be made not to alter the doses and regimens of metformin or any concomitant medications after randomization and for the duration of participation in this study, except in circumstances where a change in dose is deemed medically necessary. Any changes must be captured in the CRF. Additionally, many over-the-counter medications are also permitted during this study.

Treatments taken within 28 days before the first dose of randomized IP on Day 1 will be documented as prior treatment. Treatments taken after the first dose of randomized IP will be documented as concomitant treatment.

All concomitant treatments, both prescription and over-the-counter taken during the study must be recorded with indication, daily dose, and start and stop dates of administration. All participants will be questioned about concomitant treatment at each clinic visit.

See [Appendix 8](#) for details regarding prohibited concomitant medications. Sites are encouraged to contact the sponsor should there be questions as to whether a medication is permitted or prohibited.

Hormonal contraceptives that meet the requirements of this study are allowed to be used in participants who are women of childbearing potential (WOCBP) (see [Appendix 4](#)).

### **6.5.1. Metformin**

All participants with T2DM are required to be taking metformin monotherapy prior to inclusion in this study as listed in [Section 5.1](#). Participants must have been taking a stable dose of metformin ( $\geq 500$  mg/day) for at least 60 days prior to the screening visit (Visit 1). Participants will continue taking their own metformin at the same total daily dose that was prescribed prior to study entry through the first follow-up visit (ie, Visit 10, Week 13-14), except in circumstances where a change in dose is deemed medically necessary. For study visit days, participants should be instructed to refrain from taking morning doses at home and to bring the metformin to the site for dosing at the same time as their blinded IP. For participants taking metformin more than once a day, the timing should be approximately the same on each day.

### **6.5.2. Medications for Glycemic Control**

Aside from metformin, the use of other medications for glycemic control is not permitted in this study unless the participant meets the protocol defined glycemic rescue criteria (see [Section 8.2.4.3](#)).

### **6.5.3. Glycemic Rescue Medicine**

Participants with hyperglycemia as defined in [Section 8.2.4.3](#) should be offered glycemic rescue medication as an add on to their randomized treatment.

Glycemic rescue medication should be prescribed according to local label and obtained locally. The following glycemic rescue medications may be used: sulfonylureas, or sodium glucose co-transporter 2 (SGLT2) inhibitors. For participants who were taking a dose of metformin lower than the approved dose, increasing the metformin dose may be instituted as glycemic rescue medication, as long as the dose does not exceed the highest approved dose in the country of participation.

The following medication are NOT permitted as glycemic rescue medications: GLP-1R agonists, DPP-4 inhibitors, amylin analogues, thiazoledinediones (TZDs) or insulin.

The date of glycemic rescue medication administration as well as the name and dosage regimen of the glycemic rescue medication must be recorded on the CRF.

Participants receiving glycemic rescue medication should continue to follow all protocol specified visits and procedures according to the [SoA](#).

There is no rescue therapy to reverse the AEs observed with PF-06882961. Standard medical supportive care must be provided to manage the AEs, including administration of carbohydrates to treat HAEs (see [Section 8.2.4.2.1](#)).

### **6.5.4. Antihypertensive Medications**

The use of background antihypertensive agent(s) is permitted unless otherwise noted in [Appendix 8](#). Doses of antihypertensive agent(s) must be stable for at least 4 weeks prior to screening and throughout the study, except in circumstances where a change in dose is deemed medically necessary. Any changes in doses of these medications must be captured in the CRF.

### **6.5.5. Lipid Modifying Medications**

The use of background lipid modifying agents is permitted unless otherwise noted in [Appendix 8](#). Doses of lipid modifying agents must be stable for at least 4 weeks prior to screening and throughout the study, except in circumstances where a change in dose is deemed medically necessary. Any changes in doses of these medications must be captured in the CRF.

## **6.6. Dose Modification**

Dose titration schemes are utilized for each study intervention dosing arm in this study as described in [Section 6.1.1](#). However, each dosing regimen will be provided in blister packs, and dose adjustment will not be permitted per protocol.

## **6.7. Intervention After the End of the Study**

No intervention will be provided to study participants at the end of the study.

## **7. DISCONTINUATION OF STUDY INTERVENTION AND PARTICIPANT DISCONTINUATION/WITHDRAWAL**

### **7.1. Discontinuation of Study Intervention**

In rare instances, it may be necessary for a participant to permanently discontinue IP. If a safety or tolerability concern arises, in particular if not responsive to symptomatic management, dosing with double-blinded IP may be stopped in an individual participant at investigator discretion.

If IP is permanently discontinued, the participant remains in the study and continues to follow all protocol specified visits and procedures according to the [SoA](#).

The site should notify the Sponsor Medical Monitor or Sponsor Clinician if the below criteria for permanent discontinuation are met.

Note that discontinuation of IP does not represent withdrawal from the study.

See the [SoA](#) for data to be collected at the time of intervention discontinuation and follow-up and for any further evaluations that need to be completed.

#### **7.1.1. Criteria for Discontinuation**

Discontinuation of IP must occur for a participant meeting any of the following conditions:

- Criteria for a potential Hy's law case are met (see [Appendix 6](#)).
- Intent to become pregnant or pregnancy confirmed by serum beta human chorionic gonadotropin ( $\beta$ -hCG) testing.
- Based on mental health assessment as outlined in [Section 8.2.7](#), should be discontinued from dosing at the discretion of the investigator.

### **7.2. Participant Discontinuation/Withdrawal From the Study**

A participant may withdraw from the study at any time at his/her own request, or may be withdrawn at any time at the discretion of the investigator for safety, behavioral, compliance, or administrative reasons.

At the time of discontinuing from the study, if possible, an early termination visit should be conducted. See the [SoA](#) for assessments to be collected at the time of early termination and follow-up and for any further evaluations that need to be completed.

The early termination visit applies only to participants who are randomized and then are prematurely withdrawn from the study. Participants should be questioned regarding their reason for withdrawal. The participant will be permanently discontinued both from the study intervention and from the study at that time.

If a participant withdraws from the study, he/she may request destruction of any remaining samples, but data already generated from the samples will continue to be available, and may be used to protect the integrity of existing analyses. The investigator must document any such requests in the site study records.

If the participant withdraws from the study and also withdraws consent (see below) for disclosure of future information, no further evaluations should be performed and no additional data should be collected. The sponsor may retain and continue to use any data collected before such withdrawal of consent.

When a participant withdraws from the study because of an SAE, the SAE must be recorded on the CRF and reported on the Clinical Trial (CT) SAE Report.

Lack of completion of all or any of the withdrawal/early termination procedures will not be viewed as protocol deviations so long as the participant's safety was preserved.

### **Withdrawal of Consent:**

Participants who request to discontinue receipt of study treatment will remain in the study and must continue to be followed for protocol-specified follow-up procedures. The only exception to this is when a participant specifically withdraws consent for any further contact with him or her or persons previously authorized by the participant to provide this information. Participants should notify the investigator in writing of the decision to withdraw consent from future follow-up whenever possible. The withdrawal of consent should be explained in detail in the medical records by the investigator, as to whether the withdrawal is only from further receipt of IP or also from study procedures and/or post-treatment study follow-up, and entered on the appropriate CRF page. In the event that vital status (whether the participant is alive or dead) is being measured, publicly available information should be used to determine vital status only as appropriately directed in accordance with local law.

### **7.3. Lost to Follow-up**

A participant will be considered lost to follow-up if he or she repeatedly fails to return for scheduled visits and is unable to be contacted by the study site.

The following actions must be taken if a participant fails to return to the clinic for a required study visit:

- The site must attempt to contact the participant and reschedule the missed visit as soon as possible and counsel the participant on the importance of maintaining the assigned visit schedule and ascertain whether or not the participant wishes to and/or should continue in the study;
- Before a participant is deemed lost to follow-up, the investigator or designee must make every effort to regain contact with the participant (where possible, 3 telephone calls and, if necessary, a certified letter to the participant's last known mailing address or local equivalent methods). These contact attempts should be documented in the participant's medical record;
- Should the participant continue to be unreachable, he/she will be considered to have withdrawn from the study.

Discontinuation of specific sites or of the study as a whole is handled as part of [Appendix 1](#).

## **8. STUDY ASSESSMENTS AND PROCEDURES**

The investigator (or an appropriate delegate at the investigator site) must obtain a signed and dated ICD before performing any study-specific procedures.

Study procedures and their timing are summarized in the [SoA](#). Protocol waivers or exemptions are not allowed.

Immediate safety concerns should be discussed with the sponsor immediately upon occurrence or awareness to determine if the participant should continue or discontinue study intervention.

Adherence to the study design requirements, including those specified in the [SoA](#), is essential and required for study conduct.

All screening evaluations must be completed and reviewed to confirm that potential participants meet all eligibility criteria. The investigator will maintain a screening log to record details of all participants screened and to confirm eligibility or record reasons for screening failure, as applicable.

Every effort should be made to ensure that protocol-required tests and procedures are completed as described. However, it is anticipated that from time to time there may be circumstances outside the control of the investigator that may make it unfeasible to perform the test. In these cases, the investigator must take all steps necessary to ensure the safety and well-being of the participant. When a protocol-required test cannot be performed, the investigator will document the reason for the missed test and any corrective and preventive actions that he or she has taken to ensure that required processes are adhered to as soon as possible. The study team must be informed of these incidents in a timely manner.

For samples being collected and shipped, detailed collection, processing, storage, and shipment instructions and contact information will be provided to the investigator site prior to initiation of the study.

The total blood sampling volume for individual participants in this study is approximately 276 mL. The actual collection times of blood sampling may change. Additional blood samples may be taken for safety assessments at times specified by Pfizer, provided the total volume taken during the study does not exceed 550 mL during any period of 60 consecutive days.

### **8.1. Efficacy Assessments**

Not applicable.

### **8.2. Safety Assessments**

Planned time points for all safety assessments are provided in the [SoA](#). Unscheduled clinical laboratory measurements may be obtained at any time during the study to assess any perceived safety concerns.

#### **8.2.1. Physical Examinations**

Physical examinations are performed as indicated in the [SoA](#).

Physical examinations may be conducted by a physician, trained physician's assistant or nurse practitioner as acceptable and according to local regulation. A complete physical examination will include, at a minimum, assessments of the head, ears, eyes, nose, mouth, skin, heart and lung examinations, lymph nodes, and gastrointestinal, musculoskeletal and neurological systems.

Height will be measured at screening only.

A limited physical examination is performed at the follow-up visit and may be performed at non-specified visits if there are findings during the previous physical examination or new/open AEs, if appropriate and at investigator discretion. The limited physical examination will be focused on general appearance, lungs, cardiovascular system, and participant reported symptoms.

Investigators should pay special attention to clinical signs related to previous serious illnesses.

## 8.2.2. Vital Signs

### 8.2.2.1. Blood Pressure and Pulse Rate

In this study, assessment of vital signs (systolic blood pressure (BP), diastolic BP, and pulse rate) will occur at the nominal time points specified in the [SoA](#) per the following specifications:

- At screening, the participant's arm circumference should be measured (eg, using a flexible anthropometric tape) at the midpoint of the length of the upper arm and the appropriate cuff selected and used throughout the study.
  - **Note:** Participants with arm circumference greater than the largest cuff size available at the site or >52 cm are not eligible.
- BP and pulse rate will be measured via an automated device using an oscillometric method (not auscultation).
  - Assessment of BP and pulse rate can be manual (rather than using an automated device), only if an automated device is not available; however when done manually pulse rate must be measured in the brachial/radial artery for at least 30 seconds.
- Supine BP and pulse rate will be measured with the participant's arm supported at the level of the heart, and recorded to the nearest mm Hg, following a rest of at least 5 minutes. The assessment at Visit 3 (Day 1) will serve as the participant's baseline. Triplicate assessments will be measured at screening, and pre- and post-dose times at Visit 3, Visit 6 and Visit 9 with a brief interval (eg, 2-4 minutes) between successive triplicate assessments.
  - Same arm (preferably the dominant arm) will be used for BP and pulse rate assessments throughout the study, whenever possible.
  - Participants should be instructed not to speak during BP and pulse rate measurements.
  - See [Appendix 9](#) for proposed chronology of procedures for nominal time points when vital sign assessments coincide with other procedures.

Additional collection times, or changes to collection times of BP and pulse rate will be permitted, as necessary, to ensure appropriate collection of safety data.

### **8.2.3. Electrocardiograms**

Standard 12-Lead ECGs should be collected at times specified in the [SoA](#) section of this protocol using an ECG machine that automatically calculates the heart rate and measures pulse rate (PR), QT, and QTc intervals and QRS complex. All scheduled ECGs should be performed after the participant has rested quietly for at least 10 minutes in a supine position. Triplicate ECGs will be collected at pre- and post-dose times at Visit 3, Visit 6, and Visit 9 as specified in the [SoA](#).

If a postdose QTc interval remains  $\geq 30$  msec from the baseline and is  $> 450$  msec; or an absolute QTc value is  $\geq 500$  msec for any scheduled ECG for greater than 4 hours (or sooner, at the discretion of the investigator), or QTc intervals get progressively longer, the participant should undergo continuous ECG monitoring. A cardiologist should be consulted if QTc intervals do not return to less than the criterion listed above after 8 hours of monitoring (or sooner, at the discretion of the investigator).

In some cases, it may be appropriate to repeat abnormal ECGs to rule out improper lead placement as contributing to the ECG abnormality. It is important that leads be placed in the same positions each time to achieve precise ECG recordings. If a machine-read QTc value is prolonged, as defined above, repeat measurements may not be necessary if a qualified medical provider's interpretation determines that the QTc values are in the acceptable range.

ECG values of potential clinical concern are listed in [Appendix 7](#).

### **8.2.4. Management of Glycemic Control**

HAEs and fasting plasma glucose will be routinely monitored during participation in the study.

Based on this information, as well as review of the results reported by the central laboratory, an assessment of any symptomatic and asymptomatic occurrence of hypo- or hyper-glycemia must be undertaken.

#### **8.2.4.1. Home Glucose Monitoring**

- All participants will be provided home glucose monitoring supplies including a Sponsor-provided glucometer, instructions on the use of the glucometer and accompanying supplies.
- Home glucose monitoring logs will be provided to participants for completion at home and brought to each outpatient visit to the site along with the glucometers.
- For participants with T2DM, investigators must review the home glucose monitoring logs completed by the participants and the readings stored in the glucometer device at each visit to the site after the single-blind placebo run-in visit (Visit 2).

- For participants with obesity only, the review of the glucometer and glucose log should be completed if participants have signs or symptoms of hypoglycemia. Otherwise, regular glucometer monitoring at home is not required.
- Participants with T2DM must perform home glucose monitoring at least 3 times weekly following at least an 8- (preferably 10-) hour fast (except water). However, the investigator may recommend more frequent home glucose monitoring if needed.
- Less frequent glucose monitoring in participants with T2DM will NOT be considered a protocol deviation unless the participant fails to monitor his/her glucose for 3 or more days per week.
- If a participant experiences symptoms of hypoglycemia, home glucose monitoring should be performed, and these symptoms, along with the glucometer measurement, should be captured on the home glucose monitoring log.
- If a participant uses his/her own glucometer, and not one provided by the Sponsor, a protocol deviation will NOT be recorded provided the investigator is still able to monitor the participant's daily glucose values according to the criteria stated above.

#### **8.2.4.2. Management of Hypoglycemia**

Any episode of hypoglycemia must be captured on the Adverse Event CRF with specific details captured on the hypoglycemia Adverse Event (HAE) Form CRF. For the definition of a hypoglycemic episode and severity categorization see [Section 8.2.4.2.1](#) below.

Participants noted to have a fasting glucose value (during home glucose monitoring) meeting the definition of hypoglycemia must be instructed to repeat the measurement the next day (following at least an 8- [preferably 10-] hour fast, except water). If the second measurement also meets the below definition, participants must be asked to return to the site within 1 to 3 days (following at least an 8- [preferably 10-] hour fast, except water) and have blood collected and sent to the central laboratory for analysis of fasting plasma glucose.

#### **8.2.4.2.1. Definition and Severity of Categorization of Hypoglycemic Adverse Event (HAE)**

Based on review of the participant completed home glucose monitoring log at each site visit, as well as results reported by the central laboratory, the investigator must assess the glucose values as well as any symptoms documented.

HAE is defined as 1 of the following:

1. **Asymptomatic hypoglycemia:** An event *not* accompanied by typical symptoms of HAE but a blood glucose value of <70 mg/dL (3.9 mmol/L) using either glucometer (fingerstick blood glucose) or sponsor-identified central laboratory (plasma glucose).

2. **Documented symptomatic hypoglycemia:** An event during which typical symptoms of HAE are accompanied *with* a blood glucose value of  $<70$  mg/dL (3.9 mmol/L) using glucometer (fingerstick blood glucose) or sponsor-identified central laboratory (plasma glucose) **and** the clinical picture includes prompt resolution with food intake, subcutaneous glucagon, or intravenous (IV) glucose.
3. **Probable symptomatic hypoglycemia:** An event during which symptoms of HAE are *not* accompanied by a glucose determination but was presumably caused by a blood glucose concentration of  $<70$  mg/dL (3.9 mmol/L), **and** the clinical picture includes prompt resolution with food intake, subcutaneous glucagon, or IV glucose.

Each episode of HAE must be categorized with respect to severity. To characterize the event as severe, all 3 criteria below must be met:

1. The participant was unable to treat him/herself. Neurologic impairment, and not the age of the participant, is the explanation for why the participant could not treat him/herself and required the assistance of another person.
2. The participants exhibit at least one of the following neurological symptoms:
  - Memory loss;
  - Confusion;
  - Uncontrolled behavior;
  - Irrational behavior;
  - Unusual difficulty in awakening;
  - Suspected seizure;
  - Seizure;
  - Loss of consciousness.
3. Either:
  - If blood glucose was measured and was  $\leq 54$  mg/dL (2.7 mmol/L) using glucometer (or central laboratory); or
  - If blood glucose was not measured, the clinical manifestations were reversed by oral carbohydrates, subcutaneous glucagon, or intravenous glucose.

Events that do not meet all criteria above for severe HAE are characterized as mild or moderate in severity.

Any episode of HAE must be captured on the HAE CRF.

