**Table 1. Summary of Treatment-Emergent Adverse Events in C3421002**

	Placebo	PF-06882961 Dose a							
		10 mg BID	15 mg BID b	50 mg BID b	70 mg BID	120 mg BID	120 mg BID ST	120 mg QD	200 mg CR QD
Number of participants evaluable for TEAEs	25	9	9	10	9	9	9	8	10
Number of Participants with TEAEs	17	6	8	10	8	8	9	8	9
Number of Adverse Events	44	8	16	45	31	43	50	35	47

ST= slow titration; CR= controlled release formulation; BID = twice daily; QD = daily.

a. PF-06882961 dose reflects the randomized target dose for the group. Note that some participants in the 50 mg BID, 120 mg BID and 120 mg BID ST groups include subject(s) that, due to tolerability, did not remain on the target dose.

b. Neither the PF-06882961 15 mg BID nor the 50 mg BID dose groups received titration.

The most frequently reported TEAEs were nausea (49.0%), dyspepsia (32.7%), vomiting (26.5%), diarrhea (24.5%), headache (23.5%), and constipation (20.4%). In addition, there was 1 symptomatic hypoglycemic adverse event (AE) that was reported in 1 subject in the 120 mg BID group. This AE was non-fasting, mild in severity and of limited duration.

No deaths occurred in the C3421002 study. Two (2) participants experienced 2 severe TEAEs during the study, 1 of which occurred in the dosing period and was considered treatment related, and the other occurred during the follow-up period and was not considered treatment related. The latter participant experienced 2 non-treatment-related serious adverse events (SAEs), 1 of which occurred in the follow-up period and was a TEAE of severe intensity, and the other SAE occurred outside of the study reporting period.

While there were isolated values for laboratory tests, vital signs and electrocardiogram (ECG) intervals outside of the reference ranges, no clear adverse trends were apparent in these parameters. As has been reported for marketed GLP-1R agonists, increases in heart rate have been observed, with mean increases ranging from 5 to 15 beats per minute (bpm) across doses administered to date, and most heart rate values within the normal range.

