**Diagnostic Assessments:**

17. A PHQ-9 score  $\geq 15$  obtained at V1, V2 or V3.

18. Response of “yes” to question 4 or 5, or on any behavioral question on the C-SSRS at V1, V2 or V3.

19. Screening (Visit 1) supine blood pressure (BP)  $\geq 160$  mm Hg (systolic) or  $\geq 100$  mmHg (diastolic), following at least 5 minutes of supine rest. BP should be measured in triplicate and the average of the 3 BP values should be used to determine the participant’s eligibility. **Note:** Participants with an arm circumference greater than the largest cuff size or those with a mid-arm circumference  $>52$  cm are not eligible.

20. Screening 12-lead ECG that demonstrates clinically relevant abnormalities that may affect participant safety or interpretation of study results (eg, baseline corrected QT interval [QTcF]  $>450$  msec, complete left bundle branch block [LBBB], signs of an acute or indeterminate-age myocardial infarction, ST-T interval changes suggestive of myocardial ischemia, second- or third-degree atrioventricular [AV] block, or serious bradyarrhythmias or tachyarrhythmias).

- If QTcF exceeds 450 msec, or QRS exceeds 120 msec, the ECG should be repeated 2 more times and the average of the 3 QTcF or QRS values should be used to determine the participant’s eligibility.

21. A positive urine drug test at screening.

- **Note:** Participants who have been prescribed opiates/opioids or benzodiazepine and report the use of these drugs to the investigator at screening (Visit 1) may be allowed to participate with notification to the sponsor.

22. Participants with ANY of the following abnormalities in clinical laboratory tests at Screening, as assessed by the study specific central laboratory and confirmed by a single repeat test, if deemed necessary:

- Aspartate aminotransferase (AST) or alanine aminotransferase (ALT) level  $\geq 2 \times$  upper limit of normal (ULN).
- Total bilirubin level  $\geq 1.5 \times$  ULN.
- Fasting C-peptide  $< 0.8$  ng/mL.
- TSH  $> 1.5 \times$  ULN.

- Serum calcitonin > ULN.
- Amylase or lipase > ULN.
- Fasting plasma glucose >270 mg/dL (15 mmol/L) at screening visit (Visit 1) or single-blind placebo run-in (Visit 2).
- Estimated glomerular filtration rate (eGFR) <60 mL/min/1.73m^2 as calculated by the Chronic Kidney Disease Epidemiology Collaboration (CKD-EPI) equation.

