#### **8.2.4.3. Management of Hyperglycemia**

Hyperglycemia is defined as the following:

- Fasting blood glucose  $\geq 270$  mg/dL (15.0 mmol/L) using glucometer (or central laboratory).

After randomization, participants noted to have a fasting blood glucose value (during home glucose monitoring) meeting the above definition of hyperglycemia must be instructed to repeat the measurement the next day (following at least an 8- (preferably 10-) hour fast, except water). If the second measurement also meets the above definition, participants must be asked to return to the site a day later (following at least an 8- (preferably 10-) hour fast, except water) and have blood collected for fasting plasma glucose (and shipped to the central laboratory for analysis).

The investigator should determine if the participant collected the samples after an adequate fasting period; and if the participant is following recommended dietary guidelines. Proper dietary and collected procedures should be reinforced with the participant.

If the results from the central laboratory confirm the readings using glucometer, the participant should receive glycemic rescue medication at the discretion of the investigator (see [Section 6.5.3](#)).

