### **3.5.2. Hypoglycemic Monitoring**

Hypoglycemia AEs will be recorded in the AE Case Report Form (CRF) with details of the event captured on the Hypoglycemic Event Details CRF. Details of when these will be recorded are given in the protocol (Section 8.2.4.2).

For programming purposes, the hypoglycemic AE categories are based on the following:

- Severe Hypoglycemia: Severe is checked in the severity criteria of the CRF. This assessment will be made by the PI based on the protocol definition.
- Documented Symptomatic Hypoglycemia: If (2 – Did the participant have symptoms of hypoglycemia?) Yes and (3 – Was the blood glucose measured?) Yes and result

<70 mg/dL (or <3.9 mmol/L) on the CRF, but hypoglycemia is not classified as severe.

- Asymptomatic Hypoglycemia: If (2) No and (3) Yes and result <70 mg/dL (or <3.9 mmol/L) on the CRF, but hypoglycemia is not classified as severe.
- Probable Symptomatic Hypoglycemia: If (2) Yes and (3) No and (3a – If blood glucose was not measured, did symptoms resolve when treated with carbohydrate or glucagon?) Yes on the CRF, but hypoglycemia is not classified as severe.

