#### **6.1.1.2.9. Hypoglycemic Adverse Events**

The hypoglycemic AEs will be listed in a separate table and summarized categorically by treatment and overall as per Section 5.2.2.

CCI

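### The severe-hypoglycemia cut-off of 54 mg/dL is printed as 2.7 mmol/L; it should read 3.0 mmol/L (minor impact)

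*Protocol*

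**What the plan says.** Protocol 8.2.4.2.1 defines hypoglycemic adverse events (HAEs) and then grades them. On severity it states: "To characterize the event as severe, all 3 criteria below must be met". The criteria are, in short:

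1. The participant could not self-treat because of neurologic impairment and needed another person's help.
2. At least one listed neurological symptom was present.
3. If glucose was measured, it was at most 54 "mg/dL (2.7 mmol/L) using glucometer (or central laboratory"). If it was not measured, the signs were reversed by carbohydrate, glucagon or intravenous glucose.

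An event that misses any criterion is graded mild or moderate.

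The protocol prints other glucose limits in both units:

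- In the same section, the general HAE limit is "<70 mg/dL (3.9 mmol/L) using either glucometer (fingerstick blood glucose").
- In 8.2.4.3, hyperglycemia is defined as at least 270 "mg/dL (15.0 mmol/L) using glucometer (or central laboratory").
- In 5.2.2, exclusion criterion 22 reads "Fasting plasma glucose >270 mg/dL (15 mmol/L) at screening visit (Visit 1").

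SAP 3.5.2 takes the severe category from the severity box on the CRF and adds: "This assessment will be made by the PI based on the protocol definition". It gives no severe cut-off of its own. SAP 3.5.3.2 sets the low alert level for fasting plasma glucose at 54 mg/dL or below, in mg/dL only.

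**The concern.** One criterion carries two different cut-offs. Whenever glucose was measured, this figure is a necessary condition for the severe grade. A participant who needed help because of neurologic impairment, with a glucose between the two cut-offs, would be graded severe by a reader using mg/dL and mild or moderate by a reader using mmol/L.

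No later programmed step would catch the difference, because the SAP relies on the investigator's entry. In SAP 3.5.2 the other HAE categories apply only to events not classed as severe. A misgraded symptomatic event with a measured glucose would therefore be counted under documented symptomatic hypoglycemia instead of severe hypoglycemia.

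**Working it through.** **Conversion factor, from the protocol's own pairs**

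| Source | mg/dL | mmol/L printed | Implied mg/dL per mmol/L |
|---|---|---|---|
| Protocol 8.2.4.2.1, HAE limit | 70 | 3.9 | 70 / 3.9 = 17.95 |
| Protocol 8.2.4.3 and exclusion criterion 22 | 270 | 15.0 (15) | 270 / 15 = 18.0 |
| Protocol 8.2.4.2.1, severe criterion 3 | 54 | 2.7 | 54 / 2.7 = 20.0 |

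At 18.0 the first two pairs reproduce: 70 / 18 = 3.89, which rounds to 3.9, and 270 / 18 = 15.0. The third does not. A factor of 20 would turn 70 mg/dL into 70 / 20 = 3.5 mmol/L and 270 mg/dL into 270 / 20 = 13.5 mmol/L, contradicting both other pairs.

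**Correct value**

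- mmol/L = (mg/dL) / factor: 54 / 18.0 = 3.00. With 17.95 the result is 3.01. With 18.016, the factor from the molar mass of glucose, it is 2.997. All round to 3.0.
- In reverse, 2.7 × 18.0 = 48.6 mg/dL.
- Gap: 3.0 − 2.7 = 0.3 mmol/L, or 54 − 48.6 = 5.4 mg/dL.

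**Could rounding explain it?** A printed 2.7 covers 2.65 to 2.75 mmol/L. That is 2.65 × 18 = 47.7 to 2.75 × 18 = 49.5 mg/dL, which does not reach 54.

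**Which glucose values fall between the two cut-offs?** Dividing whole-number values by 18:

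| mg/dL | mmol/L | At most 54 mg/dL? | At most 2.7 mmol/L? |
|---|---|---|---|
| 48 | 2.67 | yes | yes |
| 49 | 2.72 | yes | no (yes if first rounded to 2.7) |
| 50 | 2.78 | yes | no |
| 51 | 2.83 | yes | no |
| 52 | 2.89 | yes | no |
| 53 | 2.94 | yes | no |
| 54 | 3.00 | yes | no |
| 55 | 3.06 | no | no |

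The conflict covers 49 to 54 mg/dL, or 50 to 54 if the converted value is first rounded to 0.1 mmol/L. On a meter showing mmol/L to one decimal, the affected readings are 2.8, 2.9 and 3.0.

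**Which figure is wrong?** The protocol leads with mg/dL and puts mmol/L in brackets as the equivalent. The SAP's low alert level independently uses 54 mg/dL. Both point to 2.7 as the error.

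**The case against.** The arithmetic has no defence; what can be argued is reach and certainty.

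- **The documents prove only that the figures disagree.** The SAP alert level concerns fasting plasma glucose, a different endpoint, so strictly 54 could be the stale figure. This is possible but unlikely, given the leading unit and the SAP value. The sponsor can confirm the intent when making the correction.
- **A reading in mg/dL is compared directly with 54 and needs no conversion.** This stands. The risk arises when a result is read or entered in mmol/L. The amendment summary says the trial takes place in the United States only, and the SAP laboratory limits are in mg/dL. However, SAP 3.5.2 accepts CRF results in mmol/L, and Protocol 8.2.4.1 tolerates participants' own glucometers, so the case cannot be excluded.
- **Affected events will be very rare.** This also stands. In the earlier 28-day study of 98 randomized participants, "there was 1 symptomatic hypoglycemic adverse event (AE) that was reported in 1 subject in the 120 mg BID group", and it was mild. Events without a glucose measurement are untouched.
- **Little depends on the grade.** Repeat testing and return to the site follow from the 70 mg/dL definition, not from severity. Every episode goes on the AE and HAE CRFs. The analysis is descriptive: "The hypoglycemic AEs will be listed in a separate table and summarized categorically by treatment and overall".

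These points fix the rating at minor. They do not make the printed figure right.

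**Conclusion.** The figure is wrong as written. At the factor the protocol uses everywhere else, 54 mg/dL is 3.0 mmol/L, and the printed 2.7 mmol/L is 5.4 mg/dL too low. This is an operative threshold in current protocol text, so it deserves correction, but the impact is minor. At most it changes the severity grade, and with it the SAP hypoglycemia category, of an event that already meets criteria 1 and 2, has a measured glucose above 48.6 and up to 54 mg/dL, and is judged by the mmol/L figure. Few or no such events are expected. No sample size, error rate, model or efficacy result depends on it. The conclusion assumes that 54 mg/dL is the intended cut-off, as the leading unit and the SAP alert level indicate.

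**What to change.** In Protocol 8.2.4.2.1, criterion 3, replace 2.7 mmol/L with 3.0 mmol/L and leave 54 mg/dL as it is. Check the HAE CRF completion instructions, which are not among the documents, and correct them if they repeat 2.7. SAP 3.5.2 contains no severe cut-off and SAP 3.5.3.2 already uses 54 mg/dL, so neither needs editing.

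The cost is one figure in a clarification letter or the next amendment, with no change to the analysis. If any HAE has already been graded using a mmol/L reading of 2.8 to 3.0, its grade should be checked against the corrected limit.
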